## Clinical Investigation Plan

### **COMPLIANCE STATEMENT:**

This clinical investigation will be conducted in accordance with this Clinical Investigation Plan, the Declaration of Helsinki, applicable Good Clinical Practices and regulations (e.g., US 21 CFR Part 50, 21 CFR Part 56, 21 CFR Part 812 and OUS ISO14155:2011) and the appropriate local legislation(s). The most stringent requirements, guidelines or regulations must always be followed. The conduct of the clinical investigation will be approved by the appropriate Institutional Review Board (IRB)/Ethics Committee (EC) of the respective investigational site and by the applicable regulatory authorities (e.g., FDA, PMDA, MHRA, etc.).

## Clinical Investigation Plan

### 1.0 INTRODUCTION

The ROSTRA study is an international, prospective, non-randomized, single-arm, multi-center, and post-market study to collect real-world safety and effectiveness data on Abbott's IonicRF™ Generator and compatible RFA accessories.

All investigators involved in the conduct of this clinical investigation will be qualified by education, training, or experience to perform their tasks and this training will be documented appropriately.

### 1.1 **Background and Rationale**

#### 1.1.1 **Background**

Chronic pain is common and debilitating. It has been linked to restrictions in mobility and daily activities, opioid dependency, anxiety and depression, and poor perceived health or reduced quality of life. Specifically, low back pain is the leading cause of years lived with disability in high to middle income countries. Patients usually undergo a treatment continuum when their pain evolves from acute to chronic; from exercise, manual therapy, and over-the-counter drugs to prescription drugs and non-invasive stimulation techniques, such as transcutaneous electrical nerve stimulation. A high proportion of subjects with chronic pain do not experience long-term benefits from these conservative treatments and seek alternative options, such as nerve blocks, and radiofrequency (RF) ablation (RFA).

Nerve blocks are injections of an anesthetic directly in the region of an affected painful nerve. A nerve block can be used therapeutically to offer short-term pain relief. Prior to RFA procedures, they are often used diagnostically to isolate the anatomical structures that are the source of pain. If the block is successful, an RFA procedure may be recommended. An RFA system is made of a RF generator, a cannula, an electrode (or probe), a grounding pad (for monopolar procedures), and an adaptor cable.

RFA is a minimally invasive procedure that conventionally uses heat generated by radio waves to target specific nerves and temporarily turn off their ability to send pain signals. Common indications are facetogenic, radicular, and sacroiliac joint pain. The Simplicity probe is specifically designed for denervation of the sacroiliac region, including peripheral nerves at S1–S4. It features three independent active areas to create a true strip lesion from a single insertion point. Other indications include knee and hip osteoarthritis, often the result of knee or hip replacements, and trigeminal neuralgia, a chronic pain condition that affects the trigeminal nerve resulting in sudden, severe facial pain.

A range of RFA procedure types can be performed. Conventional thermal RFA causes coagulative necrosis of axons in target nerves by raising the temperature above 65 degrees centigrade. Pulsed RFA is almost identical to conventional RFA, except that the current is typically carried out in 20-ms pulses every 0.5 sec at a temperature that does not exceed 42 °C. The pulsed-dose RF procedure is a technical improvement of the pulsed RF technique in which the delivery mode of the current is adapted. In monopolar mode, RF energy is applied between an electrode and the grounding pad. Monopolar RF is typically performed with multiple independent electrodes. The RF energy is applied between two electrodes in bipolar mode.

#### 1.1.2 **Rationale for Conducting this Clinical Investigation**

The IonicRF generator obtained CE mark on 31 May 2020. The European Union Medical Device Regulation (EU-MDR) 2017/745 requires that all device manufacturers provide continuous monitoring of

## Clinical Investigation Plan

the safety and effectiveness of CE marked devices. The study proposed herein is intended to fulfill the requirements set forth in the EU-MDR.

### 2.0 CLINICAL INVESTIGATION OVERVIEW

#### 2.1 Clinical Investigation Objective

The objective of this study is to collect real-world safety and effectiveness data on Abbott's IonicRF™ Generator and compatible accessories.

#### 2.2 Devices Used in the Clinical Investigation

##### 2.2.1 Name of the Device(s) Under Investigation

IonicRF RF lesion generator, along with any country-specific market-released accessory (i.e. electrode, cannula, grounding pad, and adaptor cable) compatible with the IonicRF Generator.

**Figure 1.** Components of a RF Pain Management System

##### 2.2.2 Indication for Use

The IonicRF Generator, in combination with approved compatible electrodes and cannulae, is indicated as an aid in the management of pain in the nervous system. Examples include, but are not limited to, facet denervation, rhizotomy, and related functional neurosurgical procedures.

##### 2.2.3 Description of the Device(s) Under Investigation

Please refer to the country- and device-specific IFUs for additional information regarding the devices used in this clinical investigation.

## Clinical Investigation Plan

### 2.2.4 Device Handling

The Sponsor requires all products to be stored according to the appropriate labeling and IFU as per standard practice at each center.

### 3.0 CLINICAL INVESTIGATION DESIGN

This is an international, prospective, non-randomized, single-arm, multi-center, and post-market study. Subjects will be assessed at baseline and post implant using questionnaires. Specifically, assessments will include pain intensity as assessed by the Numeric Rating Scale (NRS), quality of life as assessed by EuroQol-5 Dimensions (EQ-5D) and PROMIS-29, and procedure satisfaction as assessed by the Patient Global Impression of Change (PGIC) and patient satisfaction level. The Oswestry Disability Index (ODI), Neck Disability index (NDI), and Western Ontario and McMaster Universities Osteoarthritis Index (WOMAC) index score will be completed for specific indications only.

Subjects will be followed via clinic visit or remote follow-up at [REDACTED]. The study will enroll up to [REDACTED] subjects at up to [REDACTED] sites in Europe and the United States. No site may enroll more than [REDACTED] of the total subjects. This study uses a sample size that allows inclusion of multiple indications. Additional centers may be approached for participation in the study as needed.

It is recommended that subjects should limit increases in their prescribed chronic pain medications from Baseline to the assessment of the primary endpoint at [REDACTED]. Both the types of medication and the prescribed maximum daily dosage of pain medication for their chronic pain condition should not increase significantly (at the discretion of the investigator). If a rescue medication is required, subjects will be allowed additional aspirin or Tylenol (Acetaminophen) at a maximal dose of 2 g within a 24-hour period. (NOTE: Post-operative pain medications prescribed only for acute management of post-procedural pain are allowed.)

[REDACTED]

[figure not shown]
The Sponsor has designed this clinical investigation to involve as little pain, discomfort, fear, and any other foreseeable risk as possible for subjects. Refer to the Risks Analysis section of this clinical investigation plan for details.

## Clinical Investigation Plan

### 3.1 Clinical Investigation Procedures and Follow-up Schedule

The flowchart and the follow-up requirements of this clinical investigation are described below.

**Figure 2.** Clinical Investigation Flowchart

Clinical sites will follow subjects until the last subject completes their 6-month visit.

## Clinical Investigation Plan

### 3.2 Measures Taken to Avoid and Minimize Bias

To avoid bias, investigators are required to screen every patient scheduled for an RFA procedure with the IonicRF generator. Enrollment of consecutive subjects should be attempted.

An independent Clinical Events Committee (CEC) will adjudicate all serious and non-serious device and procedure related adverse events, and all death events. An independent expert may act as a medical monitor and evaluate X-ray or ultrasound images of the RFA procedures to verify correct cannula placement.

### 3.3 Suspension or Early Termination of the Clinical Investigation

While no formal statistical rule for early termination of the clinical investigation for insufficient effectiveness of the device under investigation is defined, the Sponsor reserves the right to discontinue the clinical investigation at any stage or reduce the follow-up period with suitable written notice to the investigator. Possible reason(s) may include, but are not limited to:

- An oversight committee (e.g., Steering Committee, Clinical Events Committee) makes a recommendation to stop or terminate the clinical investigation (such as higher frequency of anticipated adverse device effects)
- Further product development is cancelled

Should the Sponsor discontinue the clinical investigation, sites will follow subjects per routine hospital practice with device-related AEs reported to the Sponsor as per vigilance/commercial reporting requirements. The investigator shall return all clinical investigation materials (including devices) to the Sponsor and provide a written statement to the IRB/EC (if applicable). All applicable clinical investigation documents shall be subject to the same retention policy as detailed in Section 11.5 of the CIP.

A Principal Investigator, IRB/EC or regulatory authority may suspend or prematurely terminate participation in the clinical investigation at the investigational site(s) for which they are responsible. The investigators will follow the requirements specified in the Clinical Trial Agreement.

If the Sponsor suspends or prematurely terminates the clinical investigation at an individual site in the interest of safety, the Sponsor will inform all other Principal Investigators.

If suspension or premature termination occurs, the Sponsor will remain responsible for providing resources to fulfill the obligations from the CIP and existing agreements for following the subjects enrolled in the clinical investigation, and the Principal Investigator or authorized designee will promptly inform the enrolled subjects at his/her site, if appropriate.

## 4.0 ENDPOINTS

### 4.1 Primary Effectiveness and Safety Endpoint

The primary effectiveness endpoint is the relative change in Numeric Rating Scale (NRS) [REDACTED] [REDACTED] follow-up visit. NRS is the patient's self-rating of average pain intensity for the area being treated over [REDACTED] from 0 "no pain" to 10 "worst pain imaginable". This will be calculated for each represented indication.

## Clinical Investigation Plan

The primary safety endpoint is the incidence of device- and procedure-related serious adverse events.

### 4.2 Descriptive Endpoints

The following descriptive endpoints will be reported using summary statistics.

1. The following will be characterized at RFA procedure(s):
  - Overall procedure and RF time
  - A summary of Abbott RFA accessory model numbers used in the procedure
2. The following will be characterized at follow-up visits:
  - Patient reported (%) pain relief
  - Patient satisfaction
  - Patient Global Impression of Change (PGIC): to evaluate the subject's impression of change in his/her condition since the beginning of the study treatment
  - Device- and procedure-related adverse events
  - Device deficiencies
3. Change from baseline to each follow-up visit in
  - NRS (raw change); the raw change is defined as (Baseline NRS score – Follow-up NRS score)
  - EQ-5D quality of life survey, consisting of a descriptive system and the EQ VAS. The descriptive system comprises five dimensions: mobility, self-care, usual activities, pain/discomfort, and anxiety/depression. The EQ VAS records the patient's self-rated health on a vertical visual analogue scale
  - PROMIS-29 assesses pain intensity using a single 0-10 numeric rating item and eight health domains (physical function, fatigue, pain interference, depressive symptoms, anxiety, ability to participate in social roles and activities, cognitive function/abilities, and sleep disturbance) using four items per domain
  - Opioid medication usage
  - Oswestry Disability Index (ODI): 10-item scale that evaluates disability related to low-back pain (only for back pain patients)
  - Neck Disability index (NDI): 10-item scale that evaluates disability related to neck pain (only for neck pain patients)
  - The Western Ontario and McMaster Universities Osteoarthritis Index (WOMAC) index score: measures pain, stiffness, and functional limitations (only for knee and hip pain patients)
4. Relative change in NRS [REDACTED]
5. Responder analysis [REDACTED]
  - Proportion of subjects with  $\geq 30\%$  decrease on NRS
  - Proportion of subjects with  $\geq 50\%$  decrease on NRS

## Clinical Investigation Plan

### 5.0 SUBJECT SELECTION AND WITHDRAWAL

#### 5.1 Subject Population

This clinical investigation will enroll subjects of all genders from the general chronic pain population referred to participating pain clinics.

Indications include (approximately 20 subjects each):

- Lumbar facet joint pain
- Cervical facet joint pain
- Sacroiliac joint pain
- Radicular pain
- Trigeminal neuralgia
- Knee pain
- Hip pain
- Other pain

Patients must meet all general eligibility criteria and the eligibility criteria specific to the patient's chronic pain indication and provide written informed consent prior to sites conducting any investigation-specific procedures not considered standard of care.

#### 5.2 Subject Recruitment/Screening and Informed Consent

##### 5.2.1 Subject Recruitment and Screening

Potential patients presenting at the clinical site will be evaluated for study eligibility by a member of the site's clinical investigation team (physician and/or research coordinator) previously trained to the CIP. Those meeting eligibility criteria will be fully informed about the clinical study using the established Informed Consent process (described in Section 5.2.2). Subjects who do not meet the clinical investigation screening criteria are considered a screen failure and cannot participate in the clinical investigation. The Principal Investigator or the delegated clinical investigation personnel will record the screen failure in the hospital records and on a recruitment/screening log as required.

Once a duly dated and signed Informed Consent form is obtained, the clinical investigation-specific procedures may begin.

##### 5.2.2 Informed Consent

The Investigator or his/her authorized designee (if applicable) will conduct the Informed Consent process, as required by applicable regulations and the center's IRB/EC. This process will include a verbal discussion with the patient on all aspects of the clinical investigation that are relevant to the patient's decision to participate, such as details of clinical investigation procedures, anticipated benefits, and potential risks of clinical investigation participation. Sites must inform patients about their right to withdraw from the clinical investigation at any time and for any reason without sanction, penalty, or loss of benefits to which the patient is otherwise entitled. Withdrawal from the clinical investigation will not jeopardize their future medical care or relationship with the investigator.

The site shall provide the patient with the Informed Consent form written in a language that is understandable to the patient and that has been approved by the center's IRB/EC. The patient shall have adequate time to review, ask questions, and consider participation. The Principal Investigator or his/her

## Clinical Investigation Plan

authorized designee will make efforts to ensure that the patient understands the information provided. If the patient agrees to participate, they must sign and date the Informed Consent form, along with the person obtaining the consent prior to any clinical investigation-specific procedures. The site will file the signed original in the patient's hospital or research charts and provide a copy to the patient.

Sites should report any failure to obtain informed consent from a patient to the Sponsor within 5 working days and to the reviewing center's IRB/EC according to the IRB's/EC's reporting requirements.

If, during the clinical investigation, new information becomes available that can significantly affect a subject's future health and medical care, the Principal Investigator, or his/her authorized designee (if applicable) will provide this information to the subject. If relevant, sites will ask the subject to confirm their continuing informed consent in writing.

### 5.2.2.1 Special Circumstances for Informed Consent

This clinical investigation excludes individuals unable to make the decision to participate in a clinical investigation on their own or who are unable to fully understand all aspects of the investigation that are relevant to the decision to participate, or who could be manipulated or unduly influenced as a result of a compromised position, expectation of benefits or fear of retaliatory response. This clinical investigation excludes individuals under the age of 18 or age of legal consent from the clinical investigation population. The clinical investigation excludes individuals unable to read or write. The clinical investigation excludes pregnant or breastfeeding women.

In addition, sites must obtain an authorization for use and disclosure of the subject's protected health information, in accordance with the Health Insurance Portability and Accountability Act (HIPAA), from the subject or their legally acceptable representative.

## 5.3 Eligibility Criteria

Assessment for eligibility criteria is based on medical records of the site and interview with a candidate patient. Patients must meet ALL general inclusion criteria and the inclusion criteria specific to the patient's chronic pain indication to participate in the clinical investigation. If ANY general exclusion criteria or exclusion criteria specific to the patient's chronic pain indication (if applicable) are met, the patient is excluded from the clinical investigation and cannot be enrolled.

If any clinical tests are required for patient screening and are not included in a site's standard tests, they must be completed after written informed consent is obtained.

### 5.3.1 All candidate subjects

#### 5.3.1.1 Inclusion Criteria

1. Subject must provide written informed consent prior to any clinical investigation-related procedure
2. Subject is  $\geq$  18 years of age
3. Subject has chronic pain  $>$  6 months and was unresponsive to conservative management
4. Subject has pain on an NRS scale of  $\geq$  6
5. Subject is scheduled for an RFA procedure with the IonicRF generator within 30 days of baseline to treat chronic pain at one anatomical region
6. Subject has stable chronic pain medication use for 30 days

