### 5.3.2 Candidate subjects with facet joint pain (lumbar or cervical)

#### 5.3.2.1 Inclusion criteria

1. Subject has unilateral or bilateral pain on para-spinal palpation and localized pain with extension/lateral bending
2. Subject has facet joint pain confirmed by at least 1 positive medial branch block with 0.5 mL or less of anesthetics (across at least 3 vertebral levels) achieving at least 50% pain relief, with real-time injection of radiographic contrast under fluoroscopic guidance (adapted from the consensus practice guidelines; Cohen et al)

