### 5.3.3 Candidate subjects with sacroiliac joint pain

#### 5.3.3.1 Inclusion criteria

1. Subject has sacroiliac joint pain based on medical history and physical exam
2. Subject has sacroiliac joint pain confirmed by an infiltration of local anesthetics in the posterior part of the sacroiliac joint achieving at least 50% pain relief

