#### 6.2 Baseline

Baseline assessments should be completed on the same day of enrollment and after the diagnostic block(s) and/or other evaluations to determine if a subject qualifies for an RFA procedure. The diagnostic block should only be used as a diagnostic tool and its therapeutic effect should be completely nullified at the time of the baseline assessment.

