#### 6.3.2 Treatment Procedures

The following information will be collected at (each) RFA procedure:

- Procedure information (e.g., treated vertebral segments, setting, temperature, impedance, voltage)
- Overall procedure and RF time
- X-ray or ultrasound image (documentation of cannula placement)
- A summary of Abbott RFA accessory model numbers used in the procedure
- Device deficiencies (if applicable)
- Serious adverse events resulting in death (if applicable)
- Device- and procedure-related serious adverse events (if applicable)
- Device- and procedure-related adverse events (if applicable)

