#### 6.4.2.1 Numerical Rating Scale (NRS)

All subjects should answer the NRS question. The pain NRS consists of 1 question that will be asked by interviewing the subjects. Patients will be asked to rate, from 0 (no pain) to 10 (worst imaginable pain), their average pain over the past 24 hours specific to the area(s) of chronic pain being treated. A higher score indicates greater pain intensity.

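### Does letting one pain score both qualify a subject and serve as baseline distort the reported reduction enough to change the plan?

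*Protocol*

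**What the plan says.** Criterion 4 of the general inclusion criteria (Protocol 5.3.1.1, repeated in the CIP Summary) is "Subject has pain on an NRS scale of" 6 or more. It gives no source, date or recall window. Protocol 5.3 says "Assessment for eligibility criteria is based on medical records of the site and interview with a candidate patient", and Protocol 5.2.1 has candidates evaluated for eligibility before the consent discussion. A score already in the chart may therefore qualify a subject, but none is required.

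The enrollment procedures (6.1) list consent and eligibility, with no pain score. The first scheduled NRS is at baseline (6.2.1 and the Schedule of Events), and "Baseline assessments should be completed on the same day of enrollment", after any diagnostic block or other work-up for the procedure (6.2). The NRS is one interview question about "their average pain over the past 24 hours specific to the area(s) of chronic pain being treated" (6.4.2.1). The list in 6.3.2 that opens "The following information will be collected at (each) RFA procedure" contains no NRS.

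In Protocol 4.2, "the raw change is defined as (Baseline NRS score" opens a formula that subtracts the follow-up score. The same section lists responder proportions at 30% and 50% decrease. The time points of the primary endpoint (4.1) and the name of the test (8.2.1) are redacted, so baseline as the primary reference is an inference from 4.2 and the Schedule of Events.

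**The concern.** A subject chosen because one noisy rating reached 6 will on average rate lower the next time, treated or not. If that same rating is the baseline, the fall enters the change score. Nothing in the design absorbs it: there is one arm, no blinding (SAP 1.6), a null hypothesis of zero change, about 20 subjects per indication (Protocol 5.1), separate analysis by indication without multiplicity adjustment (SAP 2.10), and success tied to the primary endpoint (SAP 2.7).

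The overlap could also differ between indications. Facet pain needs "Subject has facet joint pain confirmed by at least 1 positive medial branch block" and sacroiliac pain must be "confirmed by an infiltration of local anesthetics in the posterior part of the sacroiliac joint achieving at least 50% pain relief", so some earlier pain rating is likely there. The radicular, trigeminal, knee and hip criteria require no block. At stake are the reported size of the reduction, the two responder proportions, and the chance of declaring an effect where there is none.

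**Working it through.** The plan gives no figure on this point to reproduce. The sample-size basis (Protocol 8.3) is redacted, and the check does not depend on the total of 180.

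**Inputs from the documents.** Cutoff 6 on a 0 to 10 scale; about 20 subjects per indication; 5% significance level against a two-sided alternative, so 2.5% in the favourable direction.

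**Assumed inputs, not in the documents.** Candidate-pool mean 6 to 8, SD 1.5 to 2.0, correlation r between ratings 0.5 to 0.9, one-sample t-test on relative change. Scores are rounded and clipped to 0 to 10.

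**Step 1: size by hand.** With no treatment effect and a shared rating, the spurious raw fall is about (1 − r) × (mean of qualifiers − pool mean).

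- Pool mean 6, SD 2, r 0.5: 0.5 × (7.30 − 6) = 0.65; simulated 0.68.
- Pool mean 6.5, SD 2, r 0.7: 0.3 × (7.49 − 6.5) = 0.30; simulated 0.32.
- Pool mean 7, SD 1.5, r 0.9: 0.1 × (7.43 − 7) = 0.04; simulated 0.06.

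The small excess comes from rounding and clipping. With a separate, equally correlated baseline the simulated raw fall is 0.00 at every setting.

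**Step 2: no true effect, by pool mean and share of subjects with a shared rating.** Ranges run over SD and r.

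| Pool mean | Pool below 6 | Favourable rejection, all share | Favourable rejection, half share | Relative reduction (points), all share | Relative reduction (points), half share |
|---|---|---|---|---|---|
| 6 | 37–40% | 9–29% | 4–6% | 1.6 to 8.2 | 0.4 to 1.3 |
| 6.5 | 25–31% | 6–18% | 3.3–4.8% | 1.0 to 5.8 | 0.1 to 0.4 |
| 7 | 16–23% | 4–11% | 3–4% | 0.5 to 3.8 | −0.5 to 0 |
| 8 | 5–11% | 2.5–5% | 2–3% | −0.3 to 1.0 | −1.2 to −0.2 |

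The error rate rises well above 2.5% only when most subjects share the rating and the pool lies near the cutoff. Neither condition can be read from the documents.

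**Step 3: a true effect.** With a true 30% reduction, power is at least 99.9% if all share the rating and at least 97% if half do. Compared with a separate baseline, full sharing adds 8–14, 4–8 and 1–4 points to the 30% responder proportion at pool means 6, 7 and 8.

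Not all of that gap is regression to the mean. A separate baseline may fall below 6, and small denominators pull individual ratios down: with no effect at pool mean 7, its mean relative change is −0.6 to −4.7 points rather than 0. With a true 35% reduction (pool mean 6.5, SD 2, r 0.7), the shared baseline gives 37.0% and the separate one 32.8%. The errors are 37.0 − 35 = +2.0 and 32.8 − 35 = −2.2, so about half of the 4.2-point gap belongs to the comparator.

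**Step 4: what an added score at the procedure visit would buy.** The share of raw bias removed is about (1 − r between qualifying and procedure scores) / (1 − r between qualifying and follow-up scores). The procedure is within 30 days of baseline and follow-up is at 3 and 6 months, so the first correlation is probably the higher.

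- 0.9 and 0.5: 0.1 / 0.5 = 0.20 (simulated 0.23–0.26).
- 0.7 and 0.5: 0.3 / 0.5 = 0.60 (simulated 0.61–0.67).
- Equal correlations: 1.0.

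Across procedure-visit correlations of 0.7–0.9 and follow-up correlations of 0.5–0.7, favourable rejection for raw change from the added score is 3–21% against 17–28% for a fully shared baseline at pool mean 6, 2–11% against 6–12% at 7, and 2.5–6% against 2.5–5% at 8. At 8 there is no gain.

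**The case for a change.** The best case for acting is that the baseline rating is the only scheduled pre-treatment NRS, so sharing may be the common case. If the source of the qualifying score is not captured, the overlap may be impossible to establish later. Recording its date and source costs little, and one extra question before the procedure is a light burden.

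Part of this stands. The criterion is silent, the visible protocol and SAP do not ask for the source, and the bias, where present at a pool mean of 6 to 7, runs in the favourable direction.

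The rest is weaker. Case report forms are held separately (Appendix V) and may already capture the source. Protocol 5.2.1 and 5.3 point to eligibility being judged from records and interview before consent. Baseline follows the block or other evaluations in every indication (6.2), so a difference in overlap between indications is conjecture. Writing down the date and source would document practice without altering any analysis. The extra score and its analysis would need a protocol amendment with IRB/EC handling, would leave the primary endpoint and its conclusion as they are, and could not remove placebo response or natural course, which any before-after comparison carries.

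**Conclusion.** No change to the plan follows. The missing detail is an unwritten definition that sites and case report forms can fill sensibly, and an enrollment-day baseline is a fair choice for a post-market single-arm study. A shared rating also keeps the denominator of the relative change at 6 or more, which steadies the individual ratios.

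The worst case is about 0.7 NRS points or 8 percentage points of spurious reduction with no true effect. It requires full sharing, a pool mean at the cutoff and a correlation of 0.5. If all share the rating, relative change is overstated by at most 3.8 points at a pool mean of 7 and 1.0 at 8; with half sharing, the error there is zero or slightly negative. A true reduction near 30% is detected whether all or half share the rating. The reported reduction and responder proportions should be read as before-after figures, which the declared design already implies.

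This rests on assumed pool mean, SD, correlation, test and share of subjects with a shared rating, and on the inference that baseline is the primary reference. If most subjects did share the rating and the pool did lie near 6, the reported sizes would deserve more caution.
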